## Protocol Body

### 1.0 Objectives

Primary Objectives:

[figure not shown]
1) To determine whether oral ribavirin given for therapy of Respiratory Syncytial Virus (RSV) upper respiratory tract infection (URI) can prevent its progression to Lower respiratory tract Infection (LRI)-pneumonia, when compared to aerosolized ribavirin – modified regimen in HSCT recipients at moderate or high risk for progression.

Secondary Objectives:

- 1) To determine the safety of oral ribavirin therapy when compared to aerosolized ribavirin.
- 2) To calculate the cost effectiveness of using oral ribavirin when compared to aerosolized ribavirin.
- 3) To compare RSV viral loads in nasal washes and/or other respiratory specimens and RSV neutralizing antibodies in serum between patients on both arms of the study and a observational arm where low risk patients for progression are not receiving either regimen of ribavirin.

### 2.0 Background

Over the past 2 decades, it has become apparent that community respiratory viruses (e.g. RSV, influenza, parainfluenza, picornavirus) can cause serious infections in patients with cancer, particularly in patients with acute leukemia and after hematopoietic stem cell transplantation (HSCT) recipients, resulting in substantial morbidity and mortality. They are also associated with bacterial or fungal co-infections leading to the development of respiratory super-infections. Though studies have shown that many RSV infections may resolve uneventfully without therapy, some patients do progress to LRI, increasing the morbidity and the mortality of such patients. In fact, a recent study concluded that cancer patients with RSV LRI, and with severe immunodeficiency and pre-engraftment are at high risk for RSV-attributed mortality. The use of ribavirin based regimens has been shown to halt this progression and reduce the morbidity and mortality in mainly case series from single institutions with no data from randomized or nonrandomised trials. Furthermore, in a recent systematic review on the use of ribavirin either orally, intravenously or in its aerosolized form, we determined that such therapy may halt progression of RSV from the upper to the lower respiratory tract with better survival in patients after HSCT transplantation (*Figure, Shah J and Chemaly RF, Blood, March 2011*).

Abbreviations: AR= Aerosolized ribavirin; IR= Intravenous ribavirin; OR= Oral ribavirin

Aerosolized ribavirin is the recommended therapy for RSV LRI and became the standard of care in many cancer centers. It has been used for treatment of LRI in leukemic and HSCT patients, usually in combination with IVIG. Because of the substantial morbidity and risk of fatality from LRI, ribavirin is also given pre-emptively to high-risk cancer patients with RSV URI to prevent progression to LRI. Despite its potential benefits, the drug is not routinely recommended due to inconvenience of administration, cost, and questionable efficacy because of lack of randomised controlled trials. The cost of a 10 day course of aerosolized ribavirin alone could be between \$50,000 and \$80,000, based on estimates from our financial department. While RSV infection involving only the URT may resolve uneventfully in some immunosuppressed patients, the infection can progress to the LRT with a substantial increase in mortality rate in many other patients. Hence, many of these patients who present with RSV URI are treated with aerosolized ribavirin to prevent progression. In the above mentioned systematic review, we concluded that “prompt diagnosis of RSV infection should be coupled with an aggressive approach to management in HSCT patients who have at least one identifiable risk factor for progression to LRI, such as absolute lymphocyte count (ALC) less than  $300/\mu\text{L}$  or GVHD, with early initiation of ribavirin therapy in either aerosolized or oral form before development of RSV LRI. The oral form of this drug should be explored further, as it is less expensive and probably has fewer and milder side effects than the aerosolized formulation”. It is common practice in many institutions (in the United States and Europe) to initiate oral ribavirin therapy for RSV infections in HSCT recipients instead of the aerosolized form because of all the above mentioned limitations of the latter.

We also validated a scoring system on a cohort of 284 allogeneic HSCT recipients and determined the risk of progressing to LRI and mortality based on the score assigned. Briefly, a weighted index accounting for the number and intensity of immunodeficiency markers was

developed and validated in this cohort. Adjusted relative risks calculated from Cox proportional hazards regression modeling were assigned as weights to these immunodeficiency markers; absolute neutrophil count (ANC), ALC; myeloablative chemotherapy; corticosteroids in past 30 days; GvHD; HSCT within 30 days or pre-engraftment or both; and age were utilized to generate an immunodeficiency score (ISS) (range: 0–12) for each patient. ISS scores were discretized to classify patients into low-risk (0-2), moderate-risk (3-6), and high-risk (7-12) groups. Each increased level of the ISS was accompanied by stepwise increases in the cumulative morbidity (LRI) and mortality attributable to immunodeficiency. There were significant differences in the progression to LRI and mortality ( $p<0.0001$ ) based on the scoring classification groups. RSV-targeted antiviral therapy given at the URI stage was a significant predictor of LRI and mortality. The ISS predicted the risk of these outcomes more proficiently, when the system was stratified by treatment (Table). This new ISS provides an easy, practical, and clinically applicable method of predicting the risk of progression to RSV LRI and death in allo-HSCT recipients who have or have not received antiviral therapy (*Abstract in the Proceedings of the 51th ICAAC meeting in Chicago, IL, 9/2011*). Based on these results, only patients with ISS of at least 3 (moderate to high risk) will be offered therapy for RSV URI.

|                           |              | Therapy at URI Stage |           |            | No Therapy at URI Stage |           |            | Total     |           |            |
|---------------------------|--------------|----------------------|-----------|------------|-------------------------|-----------|------------|-----------|-----------|------------|
|                           |              | %                    | n         | N          | %                       | n         | N          | %         | n         | N          |
| Progression to LRI | Low          | 6                    | 4         | 70         | 38                      | 18        | 48         | 19        | 22        | 118        |
|                           | Moderate     | 14                   | 12        | 85         | 51                      | 27        | 53         | 28        | 39        | 138        |
|                           | High         | 33                   | 5         | 15         | 100                     | 13        | 13         | 64        | 18        | 28         |
|                           | Total | 12            | 21 | 170 | 51               | 58 | 114 | 28 | 79 | 284 |
| Mortality          | Low          | 2                    | 2         | 70         | 3                       | 1         | 48         | 3         | 3         | 118        |
|                           | Moderate     | 4                    | 3         | 85         | 11                      | 6         | 53         | 7         | 9         | 138        |
|                           | High         | 20                   | 3         | 15         | 62                      | 8         | 13         | 39        | 11        | 28         |
|                           | Total | 5             | 8  | 170 | 13               | 15 | 114 | 8  | 23 | 284 |

The recommended method for ribavirin administration at our institution is a daily dose of 6g delivered at a concentration of 20 milligrams/milliliter for 18 hours daily (standard regimen) aerosolization by a small-particle aerosol generator unit (SPAG-2) via a face mask inside a scavenging tent for 5 to 10 days. A modified regimen with dose of 60 milligrams/milliliter (or 2 grams) given over 3 hours period every 8 hours for 5 to 10 days has also been used. A recent randomized trial completed at our institution showed that the probability of progression to pneumonia while on the modified regimen is less than the rate of pneumonia on the standard regimen (probability of 0.889; unpublished data; *Oral presentation at the 49th Interscience*

*Conference on Antimicrobial Agents and Chemotherapy, 2009*). Although this dosage schedule has been used, either one can be inconvenient for patients, and makes routine patient care more difficult.

Alternatively, many patients have been treated with oral ribavirin with particularly encouraging results (*Figure above*). This drug has been approved by the Food and Drug Administration (FDA) in combination with interferon alfa-2b for the treatment of Hepatitis C and it is commercially available in generic form. Although oral ribavirin was adopted as part of the armamentarium for therapy of RSV infection in immunocompromised patients in many centers in the US and Europe, further trials are necessary to demonstrate its efficacy and safety. A recent study done in Basel, Switzerland reported a total of 19 HSCT patients treated with oral ribavirin, of these 11 patients had URI, while 8 had LRI. A decrease in RSV viral loads of 2 log10 copies/mL within 7 days after treatment initiation was seen in 11 patients and none progressed to LRI or died. Another 6 patients reported a mean decrease in RSV load of 2 log10 copies/mL within 14 days of diagnosis, LRI occurred in 2 patients and 1 died. The authors also found that the rate of disease progression and mortality rate to be comparable to studies evaluating aerosolized ribavirin (*Khanna et al, CID 2008:46 407*). They further concluded that prospective, multicenter studies are needed to identify effective antiviral treatment for RSV infection among immunocompromised patient groups, where systemic ribavirin could be an option.

A systematic evaluation of oral ribavirin as an alternative therapeutic regimen for RSV infection needs to be explored. A double blind randomized comparative trial is not feasible due to the relatively small number of HSCT patients with this infection every year on the national level. We would like to conduct this phase II randomized trial to evaluate the efficacy and safety of oral ribavirin for prevention of RSV LRI when compared to aerosolized regimen ("modified regimen"). If oral use of ribavirin is as effective as the aerosolized regimen, this would be immensely beneficial to the patients as it would make the administration of ribavirin easier and more convenient and may prevent hospitalization in a good proportion of patients with tremendous impact on cost savings. Furthermore, it may increase its use and also encourage its early use in the therapy of RSV URI, which may have a favorable impact on overall morbidity and mortality in our immunocompromised patients.

### **3.0 Background Drug Information and Dosage**

Ribavirin in its oral or aerosolized form is commercially available. Drug information is provided in the attached package insert (Appendix D).

Oral ribavirin has been used at varying doses for treatment of RSV based on bioavailability and a large volume of distribution. A loading dose of 10 mg/kg orally has been used as bioavailability can range from 30-74% due to first pass metabolism (*Khanna N, et al. Clin Infect Dis. 2008;46(3):402-412*). Due to the short duration of therapy, 5 to 10 days, this will help to increase ribavirin concentration more quickly. After the loading dose, a total daily dose of 20 mg/kg/day divided into three doses given with food (max dose of 1800 mg per day). This dosing strategy falls within a previous efficacy and toxicity trial where doses between 15-45 mg/kg/day were employed (*Chakrabarti S, et al. Bone Marrow Transplant. 2001;28(8):759-763*). Efficacy and decreased toxicity were found in the lower dose cohorts 15-30 mg/kg/day.

## 4.0 Patient Eligibility

### Inclusion criteria:

4.1 HSCT patients with either moderate risk or high risk immunodeficiency based on immunodeficiency scoring system would be eligible for entry on study if a nasopharyngeal wash or throat swab specimen is positive by rapid RSV antigen testing and/or on culture within 72 hours (therapeutic arms). (Please see Appendix E for definitions and Immunodeficiency Scoring)

4.2 HSCT patients with low risk immunodeficiency based on immunodeficiency scoring system would be eligible for entry on study if a nasopharyngeal wash or throat swab specimen is positive by rapid RSV antigen testing and/or on culture within 72 hours but will not be randomized to therapeutic arms and will be followed as per standard of care (observational arm).

4.3 Patients must be at least 18 years of age and able to swallow pills.

4.4 Patients with RSV infection limited to the URT as documented by negative Chest radiographic findings within the last 48 hours of enrollment and pulse oxygenation of more than 90 mm of Hg on room air.

4.5 Women of child bearing potential with a negative urine or blood pregnancy test within a month of enrollment (only for patients who are going to be randomised to either therapeutic arms).

4.6 Patients with Hemoglobin levels more than or equal to 8 g/dl would be eligible for the study even if they are currently receiving blood products.

4.7 Patients may receive up to 2 doses of aerosolized ribavirin on the modified regimen before enrollment into the study.

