### Exclusion criteria:

4.1 Patients with previous history of hypersensitivity to ribavirin or its components

4.2 Women who are pregnant or plan a pregnancy within 8 weeks after completion of treatment (only for patients who are going to be randomised to either therapeutic arms).

4.3 Patients with evidence of RSV LRI as documented by a positive rapid RSV antigen testing and/or culture on nasal washes **AND** new or progressive infiltrates on chest radiographic studies suggestive of viral etiology and/or pulse oxygen less than 90 mm of Hg on room air.

4.4 Patients with positive RSV by rapid antigen testing and/or culture in bronchoalveolar lavage regardless of the chest radiographic findings at study entry.

4.5 Patients who are considered to be moderately or severely anemic as per the NCI classification will not be included in the study, i.e patients with hemoglobin level less than 8 g/dl.

4.6 Patients with Total Bilirubin, Aspartate Aminotransferase (AST) and/or Alanine Aminotransferase (ALT) three times the upper limit of normal.

4.7 Male partners of women who are pregnant (only for patients who are going to be randomised to either therapeutic arms).

4.8 Patients with known history of autoimmune hepatitis, Hepatitis C or those with hemoglobinopathies (eg, thalassemia major, sickle cell anemia).

4.9 Patients with creatinine clearance less than or equal to 50 ml/min.

5.0 Patients taking didanosine, azthioprine, or nucleoside reverse transcriptase inhibitors.

Patients who will be enrolled on the observational arm have to meet inclusion criteria #4.2, 4.3, and 4.4 and exclusion criteria #4.3 and 4.4 only as these patients will not receive therapy for RSV.

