## 5.0 Treatment Plan

This is an open label randomised trial. All eligible patients will be randomized to receive ribavirin therapy either at the modified schedule of 60 mg/ml of the drug for a 3-hour period 3 times/day for at least 5 days by aerosolization via a SPAG-2 generator via a face mask **OR** patients will receive a one time loading dose of 10 mg/kg oral dose then 20 mg/kg orally (rounded to the nearest 200 mg dose) divided into three doses per day at a maximum of total dose of 1800 mg/day (therapeutic arms). The duration of either regimen is recommended to be up to 10 days but could be extended for more than 10 days at the discretion of the treating physician.

In addition, patients will receive inhalational bronchodilator therapy consistent of Xopenex 0.63 mg HHN every 6-8 hours as needed and as per standard of care. Patients may receive albuterol (2.5 mg per 3ml for adults) nebulization, if Xopenex is not tolerated. Patients will not be given IVIG or palivizumab for treatment of the RSV URI. Patients who develop evidence of LRI at any time will be considered reaching the primary endpoint and will be managed at the discretion of the treating physician as per standard of care (for example, patients can be treated by the standard or the modified aerosolized regimen with or without IVIG or palivizumab).

Patients with mild immunodeficiency who are at low risk (scoring of 0-2 on ISS) for progression and when treatment is not indicated for RSV URI as per standard of care (observational arm) will be followed prospectively once a week up to 4 weeks from the diagnosis of RSV.

For schedule of events tables see PDOL appendix I.

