## **6.0 Pretreatment evaluation**

6.1 Patients will be identified based on eligibility criteria. After a patient is identified and expresses interest, the study will be explained by the study team and the informed consent form will be given to the patient to be signed.

6.2 All patients should have an initial nasopharyngeal wash positive for RSV by rapid testing and/or culture at onset of therapy unless a positive result was obtained from a specimen during the preceding 72 hours.

6.3 Routine blood tests will be obtained as per the standard of care within 48 hours of study entry as follows:

A. Hemoglobin, Hematocrit, WBC with differential if available, platelets count, pregnancy test from urine or blood for women of child-bearing potential.

B. Chemistry profile – BUN, Creatinine, Total bilirubin, Aspartate Aminotransferase (AST) and/or Alanine Aminotransferase (ALT), and alkaline phosphatase.

C. Nasal washes and blood at the time of enrollment will be taken and saved for testing for RSV viral loads and titers and neutralizing antibodies in serum at a later date (see section 7.1).

6.4 An initial history and physical examination.

6.5 A chest radiographic study (i.e. chest radiographs and/or CT scan of chest) will be obtained if not done within preceding 48 hours as per standard of care.

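### Inclusion 4.5 accepts a pregnancy test up to a month old, although a 48-hour test is already scheduled and could be the eligibility condition

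*Combined protocol and SAP*

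**What the plan says.** Four parts of the protocol bear on this point.

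- **Section 4.0, inclusion 4.5** (randomised patients only): "Women of child bearing potential with a negative urine or blood pregnancy test within a month of enrollment".
- **Section 4.0, exclusions 4.2 and 4.7** (randomised patients only): these bar "Women who are pregnant or plan a pregnancy within 8 weeks after completion of treatment" and "Male partners of women who are pregnant". Neither names a test or a time window.
- **Section 5.0:** "All eligible patients will be randomized to receive ribavirin therapy", by aerosol or by mouth. No pregnancy result is named as a precondition at this step.
- **Section 6.0 (Pretreatment evaluation), 6.3 and 6.3 A:** "Routine blood tests will be obtained as per the standard of care within 48 hours of study entry as follows", and the list includes a "pregnancy test from urine or blood for women of child-bearing potential".

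Section 7.2 then repeats the 6.3 tests at least weekly on the therapeutic arms.

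**The concern.** Inclusion 4.5 is the only supplied rule that requires a negative pregnancy result, and that result may be up to a month old. Pregnancy status can change within that time. A fresher test is already on the schedule, but nothing in the supplied text makes its result a condition for randomisation or dosing.

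Both therapeutic arms give ribavirin, and the exclusions show that the protocol means to keep pregnancy out of those arms. Whether it succeeds depends on each site reading inclusion 4.5, section 6.3 A and exclusion 4.2 together and in the right order. At stake is patient safety. The statistical design is not affected.

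**Working it through.** The plan gives no figure to reproduce. The check compares the rules and follows one patient through them.

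**1. The rules side by side**

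| Place | Timing | Negative result required? | Result known before randomisation or dose? |
|---|---|---|---|
| Inclusion 4.5 | Within a month of enrolment | Yes | Not stated |
| Section 6.3 A | Within 48 hours of study entry, before or after not stated | Not stated | Not stated |
| Exclusion 4.2 | None | No test named | Works only if the pregnancy is known |
| Section 7.2 | At least weekly on study | Not stated | Too late for the first dose |

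The randomisation text in section 11.0 adds no condition. Elsewhere in section 6.0 the direction of a window is given: 6.2 and 6.5 both refer to a preceding period (72 and 48 hours). Section 6.3 does not do this. Other time-limited eligibility facts also have short windows: 72 hours for RSV positivity (inclusion 4.1) and 48 hours for chest imaging (inclusion 4.4).

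**2. One patient followed through the rules**

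Take a woman whose negative test is three weeks old and who is now pregnant without knowing it. She meets inclusion 4.5.

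- If the 6.3 A test is done and read before randomisation, it is positive, exclusion 4.2 applies and she is not randomised.
- If the 6.3 A test is pending at randomisation, or is drawn after entry but inside 48 hours, exclusion 4.2 has no known pregnancy to act on. No supplied sentence holds back randomisation or the first dose.
- If the positive result arrives after dosing starts, sections 9.1 to 9.3 do not list pregnancy as a reason to stop.

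The gap is therefore confined to a pending or late 48-hour test.

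**3. What the change would and would not cover**

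Inputs: 3 doses a day (section 5.0); 5 to 10 days (sections 2.0 and 3.0); one loading dose in the oral arm (section 5.0).

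- Shortest course: 3 × 5 = 15 doses.
- Ten-day course: 3 × 10 = 30 doses.
- Oral arm with the loading dose: 15 + 1 = 16 to 30 + 1 = 31 doses. Either arm has more if therapy is extended.

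A known negative result would come before all of these. They are dose counts for any treated patient and do not estimate how many women would be exposed.

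Inclusion 4.7 sets a limit on the change: "Patients may receive up to 2 doses of aerosolized ribavirin on the modified regimen before enrollment into the study". Section 2.0 describes the modified regimen as "given over 3 hours period every 8 hours for 5 to 10 days". Two consecutive doses then take 8 + 3 = 11 hours from the start of the first to the end of the second. Since 11 hours is less than 48 hours, a test inside the 48-hour window may fall before or after those doses. The change therefore does not guarantee a test before any ribavirin at all.

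**The case against.** The best case for leaving the text alone has five parts.

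- **Eligibility includes the exclusions.** A pregnant woman is ineligible under exclusion 4.2 however old her negative test is. This is right, and it means that the protocol nowhere permits treating a pregnant woman. But exclusion 4.2 names no test, so it acts only on a pregnancy that is already known.
- **Section 6.0 is headed as pretreatment, and its panel supplies the haemoglobin, liver and creatinine values for other exclusions.** Those criteria also lack a rule that the result be known first. This is a fair reading of the intended order, and it is why most cases would be caught. Pregnancy differs in one respect: inclusion 4.5 expressly accepts an older result than the one already scheduled.
- **Section 7.2 repeats the tests weekly.** On its face this includes the pregnancy test and would help later detection. It comes too late to protect the first doses.
- **Appendix D (package insert) and appendix I (schedule of events) may contain a pre-dose rule.** They may; neither was available. Inclusion 4.5 would then still need its wording aligned.
- **The change is partial and could delay treatment that the background section wants started early.** Both points stand. Doses before enrolment are not reached, and a short wait for a result is possible.

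Together these points make the issue small. They do not give a reason to keep the one-month window.

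**Conclusion.** The point holds as a minor, optional improvement to patient safety. The supplied text lets the pregnancy criterion be met on a result up to a month old, and it does not tie the 48-hour test to randomisation or the first study dose. The rules do not contradict each other, and normal site practice would catch most cases.

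The difference is one of wording: a month against 48 hours. No exposure can be estimated, because the documents do not give the number of women of child-bearing potential. Sample size, power and the primary analysis are unaffected. Confidence is medium, because the conclusion assumes that appendices D and I contain no pre-dose pregnancy rule. If they do, what remains is an inconsistency to tidy in 4.5.

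**What to change.** Make two wording edits:

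1. In inclusion 4.5, require a negative urine or blood pregnancy test within the 48 hours before randomisation to a therapeutic arm, with the result known before randomisation and before the first study dose.
2. In section 6.3 A, state that this is the same test.

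The test is already scheduled, so no procedure is added. The cost is a possible short wait for the result before randomisation. The edits do not cover aerosolized doses given before enrolment under inclusion 4.7.
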